#### **9.2 Study completion and post-study treatment**

Study completion is defined as when the last patient finishes their last follow-up visit and any assessments associated with this visit have been documented and followed-up appropriately by the Investigator or, in the event of an early study termination decision, the date of that decision.

Following the end of treatment or early treatment discontinuation, patients will enter in the Follow-up Period unless unfeasible (e.g. consent withdrawal, patient lost to follow-up). Patient visits and assessments will be performed during the follow-up period as per the study schedule of assessments ([Table 8-2](#)) and [Section 9.1.1](#).

The last follow-up visit (5 years after the last dose of Lutathera) will be considered as End of Study (EoS) visit for each patient.

When the study planned enrollment is met, study subjects currently on study treatment or in the follow-up period will continue the study as per the study schedule of assessment ([Table 8-2](#)).

Study Treatment will not be provided to the enrolled patients after completion of the study as Lutathera is administered as 4 doses and this is a full regimen. No provision of Lutathera post-trial is considered necessary.

### **10 Safety monitoring and reporting**

#### **10.1 Definition of adverse events and reporting requirements**

##### **10.1.1 Adverse events (AE)**

An adverse event (AE) is any untoward medical occurrence (e.g. any unfavorable and unintended sign [including abnormal laboratory findings], symptom or disease) in a clinical investigation participant after providing written informed consent for participation in the study. Therefore, an AE may or may not be temporally or causally associated with the use of a medicinal (investigational) product.

The investigator has the responsibility for managing the safety of individual participant and identifying adverse events.

Sponsor qualified medical personnel will be readily available to advise on trial related medical questions or problems.

Adverse events that begin or worsen after informed consent must be recorded in the Adverse Events eCRF. Conditions that were already present at the time of informed consent must be recorded in the Medical History page of the subject's eCRF. Adverse events (including lab abnormalities that constitute AEs) must be described using a diagnosis whenever possible, rather than individual underlying signs and symptoms. When a clear diagnosis cannot be identified, each sign or symptom must be reported as a separate Adverse Event.

The occurrence of adverse events must be sought by non-directive questioning of the participant at each visit during the study. Adverse events also may be detected when they are volunteered by the participant during or between visits or through physical examination findings, laboratory test findings, or other assessments.

Adverse events must be recorded under the signs, symptoms, or diagnosis associated with them, accompanied by the following information (as far as possible) (if the event is serious refer to [Section 10.1.2](#); if the event is adverse event with special interest (AESI) refer to [Section 10.1.5](#)):

1. The Severity grade OR the Common Toxicity Criteria (CTC) AE grade ([Appendix 3](#)).
  - a. If “severity grade” is selected, include the following:
    - i. mild: usually transient in nature and generally not interfering with normal activities
    - ii. moderate: sufficiently discomforting to interfere with normal activities
    - iii. severe: prevents normal activities
  - b. If “CTCAE grade” is selected, include the following:
    - i. Adverse events will be assessed and graded between 1 to 5.
2. The investigator is obligated to assess the relationship between any treatment used in the study (study treatment, AxMPs) and each occurrence of each AE. The investigator will use clinical judgment to determine the relationship. A reasonable possibility of a relationship conveys that there are facts, evidence, and/or arguments to suggest a causal relationship, rather than a relationship cannot be ruled out. Alternative causes, such as underlying disease(s), concomitant therapy, and other risk factors, as well as the temporal relationship of the event to study intervention administration, will be considered and investigated. For causality assessment, the investigator will also consult the IB and/or product information, for marketed products. The causality assessment is one of the criteria used when determining regulatory reporting requirements.
3. Its duration (start and end dates) or if the event is ongoing, an outcome of not recovered/not resolved must be reported.
4. Whether it constitutes a Serious Adverse Event (see [Section 10.1.2](#) for definition of SAE) and which seriousness criteria have been met.
5. Action taken regarding study treatment
  - Dose not changed
  - Dose reduced

- Drug interrupted/withdrawn

6. Treatment for adverse events. All adverse events must be treated appropriately.

7. Its outcome i.e., its recovery status or whether it was fatal

If the event worsens, it should be reported a second time in the eCRF noting the start date when the event worsens in toxicity. For grade 3 and 4 adverse events only, if improvement to a lower grade is determined a new entry for this event should be reported in the eCRF noting the start date when the event improved from having been Grade 3 or Grade 4.

Once an adverse event is detected, it must be followed until its resolution (or until it is judged to be permanent) or until 30 days after end of study visit. Assessments must be made at each visit (or more frequently, if necessary) of any changes in severity, the suspected relationship to the interventions required to treat it, and the outcome.

For the investigational product and for non-authorized AxMPs (when applicable), information about adverse drug reactions and how to manage them can be found in the Investigator's Brochure (IB) or equivalent documentation. Information about adverse drug reactions can also be found in the product information for marketed products.

Abnormal laboratory values or test results constitute adverse events only if they fulfill at least one of the following criteria:

- they induce clinical signs or symptoms
- they are considered clinically significant
- they require therapy

Clinically significant abnormal laboratory values or test results must be identified through a review of values outside of normal ranges/clinically notable ranges, significant changes from baseline or the previous visit, or values which are considered to be non-typical in participant with the underlying disease.

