The observed effects of short-term bone marrow toxicity after Lutathera treatment are anemia, thrombocytopenia, leukopenia, lymphopenia and neutropenia, which are usually mild and transient ([Strosberg et al 2017](#), [Lutathera USPI](#)). In the Lutathera arm of the NETTER-1 study, grade 3 or 4 anemia, thrombocytopenia, leukopenia, lymphopenia and neutropenia occurred in 0%, 1%, 2%, 44% and 3% of patients, respectively ([Lutathera USPI](#)). Lymphopenia in the Lutathera arm was not associated with an increased rate of infections compared to the control arm. Overall, it is important to note that the observed lymphopenia following PRRT is not a major concern regarding risk of infections, since only B lymphocytes are transiently affected, a subtype which is not directly involved in infection defense ([Sierra et al 2009](#)). The median time to onset of hematological toxicities was during the 2nd - 3rd cycle of Lutathera, while the median time of resolution was within 6 months after the last Lutathera cycle. When hematological toxicity occurred, a trend towards stabilization followed by improvement in patients with longer follow-up was observed.

Based on the median time to onset and the resolution time of hematological toxicities observed in adults in the NETTER-1 study, the short-term follow-up period in this study is 6 months after the last dose of Lutathera. This will allow for evaluation of cumulative toxicities after 4 cycles of Lutathera and for the detailed observation of resolution of hematological toxicity cases.

As for any radiotherapy, one of the long-term safety risks of Lutathera treatment is secondary malignancies. In the NETTER-1 study, with a median follow-up time of 24 months, myelodysplastic syndrome (MDS) was reported in 3 patients (2.3%) receiving Lutathera with long-acting octreotide compared to no patients receiving high-dose long-acting octreotide. In the Erasmus MC study, 16 patients (2%) developed MDS and 4 (0.5%) developed acute leukemia. The median time to the development of MDS was 28 months (9 to 41 months) for MDS and 55 months (32 to 125 months) for acute leukemia ([EU SmPC](#)).

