### On-treatment assessment/event and observation periods

For adverse event reporting, the overall observation period will be divided into three mutually exclusive segments:

1. **Screening period:** from day of patient's informed consent to the day before first administration of study treatment
2. **on-treatment period:** from date of first administration of study treatment to 56 days (i.e. 8 weeks) after date of last actual administration of study treatment (including start and stop date).
3. **short-term follow-up period:** from day 57 after last administration of study treatment to day 183 (6 months) after date of last administration of study treatment
4. **long-term follow-up period:** starting from day 184 after last administration of study treatment

Safety summaries (tables, figures) include data from either on-treatment, short-term and long-term follow-up periods cumulatively with the exception of selection period data or baseline data which will also be summarized where appropriate. In particular, summary tables for adverse events (AEs) will summarize only on-treatment events, with a start date during the on-treatment period (**treatment-emergent** AEs) and specific listings of related SAEs and adverse events of special interest (AESI) will be provided for the short-term and long-term follow-up periods.

However, all safety data (including those from the short-term and long-term follow-up periods) will be listed and those collected during the short-term and long-term follow-up periods will be flagged.

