### 2.6.1 Adverse events (AEs)

AE summaries will include all AEs occurring during on-treatment period. Specific listings will also be presented for the SAEs and AESIs occurring during short-term and long-term follow-up. All AEs collected in the AE eCRF page will be listed along with the information collected on those AEs e.g. AE relationship to study drug (separately for AEs related to any study drug, related to Lutathera and related to amino acid solution), AE outcome etc. The starting period of

the AEs (screening period, on-treatment, short-term and long-term follow-up periods) will be flagged in the listings.

AEs will be summarized by number and percentage of participants having at least one AE, having at least one AE in each primary SOC and for each PT. AEs will be coded using the MedDRA and assessed according to the CTCAE version 5.0. A participant with multiple occurrences of an AE will be counted only once in the respective AE category. A participant with multiple CTCAE grades for the same PT will be summarized under the maximum CTCAE grade recorded for the event. AE with missing CTCAE grade will be included in the 'All grades' column of the summary tables. In AE summaries, the primary SOC will be presented alphabetically, and the PTs will be sorted within primary SOC in descending frequency. The sort order for the PT will be based on their frequency in the total column.

The following AE summaries will be produced based on the FAS:

- Overview of adverse events and deaths (number and % of patients who died, with any AE, any SAE, any dose reductions/interruptions, any fatal SAEs, etc.);
- AEs regardless of study drug relationship by SOC, PT, and severity;
- AEs suspected to be study drug related by SOC, PT, and severity;
- AEs leading to discontinuation regardless of study drug relationship by SOC, PT, and severity;
- SAEs regardless of study drug relationship by SOC, PT, and severity;
- AEs leading to dose interruption/adjustment by SOC, PT, and severity;
- SAEs suspected to be study drug related by SOC, PT, and severity;

In addition, all AEs and SAEs with a start date in the short term and long-term follow-up will be listed separately.

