#### **2.6.1.1 Adverse events of special interest / grouping of AEs**

During the treatment period, all AESIs are to be reported to the Sponsor irrespective of causality. During the follow-up period, AESIs are to be reported only if considered related to the study treatment except for all secondary malignancies which need to be reported as AESIs irrespective of causality. The AESIs represent main risks of Lutathera and amino acid treatment reported in adults, as well as potential risks in pediatric population.

The selection of the AESIs will be initially based on the classification of the AEs as reported in the Adverse Event eCRF page.

Additional groupings of AESIs above and beyond those flagged in the eCRF may also be examined in this study. These groupings are defined using MedDRA terms, SMQs (standardized MedDRA queries), HGLTs (high level group terms), HLT (high level terms) or PTs. Customized SMQs (Novartis MedDRA queries, NMQ) may also be used. A NMQ is a customized group of search terms which defines a medical concept for which there is no official SMQ available or the available SMQ does not completely fit the need. It may include a combination of single terms and/or an existing SMQ, narrow or broad.

The grouping of AEs in AESI according to project standards will be specified in the electronic Case Retrieval Strategy (eCRS) or separate listing in case of the AESI category is not included in the eCRS, and may be regularly updated.

All AESI categories will be summarized for those events occurring on-treatment. Events starting during the short-term and long-term follow-up periods will be listed.

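### A grade 3–4 adverse event that improves after day 56 is listed as starting in follow-up, because improvement opens a newly dated entry and the SAP does not link entries

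*Protocol*

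**What the plan says.** **Recording.** For grade 3 and 4 events, Protocol 10.1.1 says that "if improvement to a lower grade is determined a new entry for this event should be reported in the eCRF noting the start date" on which the event improved. The same section asks that every AE be followed until it resolves, is judged permanent, or 30 days have passed since the end-of-study visit.

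**Assignment to periods.** SAP 2.1.1 runs the on-treatment period from the first administration "to 56 days (i.e. 8 weeks) after date of last actual administration of study treatment". Short-term follow-up covers days 57 to 183 after the last administration, and long-term follow-up starts on day 184. AE summary tables "will summarize only on-treatment events, with a start date during the on-treatment period", and the SAP calls those events treatment-emergent. SAP 2.6.1 adds that "all AEs and SAEs with a start date in the short term and long-term follow-up will be listed separately", and that the starting period of "the AEs (screening period, on-treatment, short-term and long-term follow-up periods) will be flagged in the listings". For AESIs, SAP 2.6.1.1 says: "Events starting during the short-term and long-term follow-up periods will be listed".

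**Joining entries.** SAP 2.6.3 counts consecutive entries with the same SOC and PT once when the gap is one day or less, but this is written for the two on-treatment registry tables. SAP 2.6.1 counts a participant once per AE category, at the maximum grade. That rule works in summary tables, not in listings.

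**The concern.** One clinical event can become two records, the second dated at its improvement. A rule that reads only start dates cannot tell that second record from a new event.

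This matters most in follow-up. Two secondary endpoints are AE incidence up to 6 months after the last dose and AE incidence during long-term follow-up. For these the SAP plans AE listings and, apart from the summary of all deaths in SAP 2.6.2, no AE tables. Anyone counting delayed toxicity will therefore count from listings in which an improvement can look like a late onset.

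The same rule reaches a co-primary endpoint by a narrower route. An event that began before dose 1 and improved after it has an entry that starts on treatment.

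**Working it through.** No figure in the plan is in dispute, so the check applies the stated rules to example events.

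**1. Events that start on treatment.** Inputs: the SAP 2.1.1 cut-points (days 56/57 and 183/184 after the last dose), the Protocol 10.1.1 entry rule, and, for illustration only, a grade 3 event starting on day 35 after the last dose.

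| Day of improvement after last dose | Period of grade 3 entry | Period of lower-grade entry |
|---|---|---|
| 50, 56 | on-treatment | on-treatment |
| 57, 63, 91, 133, 175 | on-treatment | short-term follow-up |
| 190 | on-treatment | long-term follow-up |

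These days correspond to scheduled visits. The End of Treatment visit is at 8 weeks ± 1 week, so it can fall as late as 9 × 7 = day 63. The short-term visits at weeks 13, 19 and 25 fall on 13 × 7 = 91, 19 × 7 = 133 and 25 × 7 = 175. Protocol 4.3 reports for haematological toxicity in adults that "the median time of resolution was within 6 months after the last Lutathera cycle". Six months is 6 × 30.4375 = 182.6 days, so the window from day 57 to day 183 lies inside that span.

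**2. Which improved events are still recorded in follow-up.** Protocol 8.4.1 limits follow-up recording to related SAEs and AESIs, plus all secondary malignancies. Protocol 10.1.5 then decides what remains an AESI at the lower grade:

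- Thrombocytopenia is an AESI from grade 2, so a related event improving from grade 3 to grade 2 still qualifies.
- Suspected endocrine and bone toxicities qualify at any severity. Nephrotoxicity has no CTCAE grade threshold.
- Other haematotoxicity qualifies at grade 3–4, or at any grade with clinical consequences. Neutropenia or lymphopenia that improves to grade 2 without such consequences no longer meets the definition. The documents do not settle whether its improvement entry is then made, because 10.1.1 still asks for the event to be followed.

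**3. Effect on on-treatment tables.** If an event starts after dose 1 and both entries fall on treatment, the participant is counted once at the maximum grade. If the second entry falls in follow-up, the first is still counted. Incidence is unchanged either way.

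**4. Events that start before dose 1.** Take a grade 3 AE that begins after consent and before dose 1, and improves to grade 2 during cycle 1.

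- The first entry starts in screening and is not tabulated.
- The second entry starts on treatment. It meets the start-date definition in SAP 2.1.1 and falls in the first-cycle AE summary of SAP 2.5.2, reading occurrence there by start date.
- Once-per-participant counting gives no protection if this is the participant's only on-treatment entry for that PT.
- The Adverse events part of Protocol 12.5.2 requires a start after the first dose, or an event already present that increased in severity. This event does neither.

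The opening text of Protocol 12.5.2 also uses start date alone, so the protocol contains both formulations. SAP section 4 declares no change from the protocol's analyses, so the difference is not a declared departure.

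**The case against.** The strongest reply is that little is lost. The protocol describes the record as a new entry for the same event, so a sensible programmer would not treat it as a new onset. Both records appear in the full AE listing, and with 11 patients enrolled at Amendment 03 they can be matched by hand. Laboratory toxicities are graded programmatically from observed values, so that evidence, including haematological recovery, does not depend on AE entries. The entry rule is worded as a recommendation. Full resolution is captured by an end date and outcome, so only partial improvement clearly creates a second entry. For neutropenia and anaemia, Table 6-4 withholds the next dose until grade 0–2, so events before a later dose should improve on treatment. The pre-dose route is narrow, because conditions present at consent go to medical history.

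Most of this stands and limits the size of the point. It does not remove it. The period flag and the separate follow-up listings follow start date as the SAP is written, and matching by hand is neither planned nor required.

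A reader might multiply the 44% adult rate of grade 3–4 lymphopenia in Protocol 4.3 by the number enrolled and take the result as the number misfiled. The documents do not support that. It would count patients who have the event, not patients whose event first improves after day 56, and lymphopenia improved to grade 2 generally falls below the AESI threshold. Nor does the resolution time in Protocol 4.3 show that several events would be affected: it is an upper bound on a median, and it concerns resolution rather than first improvement.

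**Conclusion.** The point holds in a limited form. Under the stated rules, an on-treatment grade 3–4 event that improves but does not resolve after day 56, and is still recordable, is flagged and listed as starting in follow-up. Clear examples are related thrombocytopenia at grade 2 and related nephrotoxicity, endocrine or bone AESIs. Separately, a grade 3–4 AE arising between consent and dose 1 that improves in cycle 1 would enter the first-cycle table, contrary to the more specific protocol definition.

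The number of affected patients cannot be derived from the documents. A reader might infer that on-treatment AE rates are inflated. For events starting after dose 1 they are not. Nor can the follow-up effect be expressed as a percentage error in a planned table, because follow-up AEs are listed and not tabulated.

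The conclusion assumes that sites follow the entry rule and that the SAP is programmed as written. The change is worth making because the listings carry the follow-up AE endpoints and the correction is cheap.

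**What to change.** In SAP 2.1.1 and 2.6.1:

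- Link split entries of one event, by an eCRF parent identifier if there is one, otherwise by same participant and PT with contiguous dates.
- Assign the period from the start date of the first linked entry.
- Count a later entry as new or treatment-emergent only if the grade rises, in line with the Adverse events part of Protocol 12.5.2.
- Use improvement entries only for duration and outcome.

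Apply the same rule to the AESI listings in SAP 2.6.1.1 and the first-cycle summaries in SAP 2.5.2. The cost is SAP wording and one linking step in the AE dataset. The recording rule in Protocol 10.1.1 can stay, and no new data are needed. The final analysis waits for the 5-year follow-up, so the rule can still govern it.

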#### Reporting of AEs related to AxMP(s):

All AEs related to any authorized auxiliary medicinal product used in this study must be reported to Advanced Accelerator Applications. In assessing causality, the investigators will use the points above.

If a suspicion that medical occurrence could be related to study treatment (and/or interaction with study treatment cannot be ruled out), the reporting rules for study treatment apply.

AxMP safety reporting requirements will only apply once the trial has been transitioned under EU Clinical Trial Regulation 536/2014.

#### **10.1.2 Serious adverse events (SAE)**

An SAE is defined as any adverse event [appearance of (or worsening of any pre-existing)] undesirable sign(s), symptom(s), or medical conditions(s) which meets any one of the following criteria:

- fatal

- life-threatening. Life-threatening in the context of a SAE refers to a reaction in which the participant was at risk of death at the time of the reaction; it does not refer to a reaction that hypothetically might have caused death if it were more severe (refer to the [ICH-E2D Guidelines](#)).
- results in persistent or significant disability/incapacity
- constitutes a congenital anomaly/birth defect
- requires inpatient hospitalization or prolongation of existing hospitalization, unless hospitalization is for:
  - routine treatment or monitoring of the studied indication, not associated with any deterioration in condition
  - elective or pre-planned treatment for a pre-existing condition that is unrelated to the indication under study and has not worsened since signing the informed consent
  - social reasons and respite care in the absence of any deterioration in the participant's general condition
  - treatment on an emergency outpatient basis for an event not fulfilling any of the definitions of a SAE given above and not resulting in hospital admission
- is medically significant, e.g. defined as an event that jeopardizes the participant or may require medical or surgical intervention to prevent one of the outcomes listed above

Medical and scientific judgment should be exercised in deciding whether other situations should be considered serious reactions, such as important medical events that might not be immediately life threatening or result in death or hospitalization but might jeopardize the participant or might require intervention to prevent one of the other outcomes listed above. Such events should be considered as “medically significant.” Examples of such events are intensive treatment in an emergency room or at home for allergic bronchospasm, blood dyscrasias, or convulsions that do not result in hospitalization or development of dependency or abuse (refer to the [ICH-E2D Guidelines](#)).

All new malignant neoplasms will be assessed as serious under “medically significant” if other seriousness criteria are not met and the malignant neoplasm is not a disease progression of the study indication.

Any suspected transmission via a medicinal product of an infectious agent is also considered a serious adverse reaction.

All reports of intentional misuse and abuse of the product are also considered serious adverse event irrespective if a clinical event has occurred.

Treatment-emergent elevations in AST or ALT ( $> 3 \times \text{ULN}$ ) in combination with total bilirubin  $> 2 \times \text{ULN}$  or jaundice in the absence of cholestasis (defined as ALP  $< 2 \times \text{ULN}$ ) or other causes of hyperbilirubinemia can be an indicator of severe drug induced liver injury (Hy's Law). The Hy's Law criteria may be changed to increases of transaminases 2-fold above baseline values for subjects with elevated baseline values. For this reason, a potential Hy's Law case requires expedited reporting, and will be handled as a serious unexpected adverse event

(assessing it as medically significant in the absence of any other seriousness criteria). It must be reported as an SAE to the sponsor promptly (i.e., even before all other possible causes of liver injury have been excluded). Reporting should include all available information, especially that needed for evaluating the diagnosis, severity and likelihood that the study treatment caused the reaction. For patient monitoring and to better understand potential etiologies, the investigator must initiate a close follow-up until complete resolution of the problem and completion of all attempts to obtain supplementary data.

